4.6. Multiple Comparisons/Multiplicity

Since this is an exploratory proof of concept study, no formal testing strategy or adjustments of p-values will be employed. Estimates and confidence intervals (CIs) for treatment groups and from pairwise comparisons will be used in an exploratory manner.

4.7. Data Handling

4.7.1. **Baseline Definitions or Conventions**

Unless, as specified in Section 3.3.2.1, the Screening period is used to derive a Baseline value, then Baseline value is defined as the Day 1 (randomization) measurement. If the Day 1 measurement is not available, the last non-missing pre-randomization measurement will be used as the Baseline value. For vital signs, where the time of the assessment is available, the last pre-treatment assessment on Day 1 will be the Baseline value.

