3.3.2. Exploratory Endpoints

3.3.2.1. Abdominal Pain Score (APS) and Average Abdominal Pain Score (AAPS)

The APS is a PRO using a numerical rating scale (NRS) which is recorded in a subject diary. The 11-point NRS scale ranges from 0 (no abdominal pain) to 10 (worst possible abdominal pain) will be recorded by subjects in a diary as follows;

During Screening Period

APS is recorded twice daily for at least 7 consecutive days within the Screening period (Day -28 to Day -1), at the following times:

- 1. Early morning, approximately 06:00 08:00
- 2. Late evening, approximately 20:00 22:00

To establish a baseline for AAPS the following procedure will be adopted:

The last diary entry prior to treatment will be identified. The 7 consecutive days that terminate with this last data point constitute the Screening reference period. Baseline for AAPS is the mean of non-missing pain scores within the Screening reference period.

During Treatment Period

APS is recorded three times a day on each treatment Day (Day 1 to 56) at the following times:

- 1. Before the morning dose and before any other morning dose study procedures (i.e., at trough APD371 concentration)
- 2. Approximately 1.5 hours after the morning dose (i.e., at peak APD371 concentration)
- 3. Before the evening dose (i.e., at evening trough ADP371 concentration)

Note: Subjects will also be required to complete the diary before their first morning dose on Wk 0 (Day 1), and at the EOT Visit at Wk 8 in the early morning (06:00 - 08:00). If a subject discontinues the study, ET, the APS score will be assessed.

It should be noted that:

- The AAPS is derived for each assessment period (Wks 1, 2, 4, 6, 8). For Wks 4, 6, and 8 scores are collected from the previous 7 days of diary entries prior to the visit day. 'Peak AAPS' is the mean of non-missing APS recorded at the time of peak concentration for those 7 days. Likewise, 'Trough APS' is the mean of non-missing APS recorded at the time of trough concentration for those 7 days. Similarly, 'Evening Trough APS' is the mean of non-missing APS recorded at the time of evening trough concentration for those 7 days. Wk 1 and Wk 2 peak, trough, evening trough, and overall AAPS are derived in a similar manner but note that:
 - For Wk 1, as Day 1 is neither peak nor trough, and APS scores cannot be accurately identified as pre-dose or post-dose, scores on Day 1 are disregarded. Hence, AAPS scores may be obtained from fewer than 7 days.

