4.3. Randomization and Stratification

Subjects will be randomized after the Investigator has verified that they are eligible per criteria in Section 3.5 and Section 3.6 of the protocol. Subjects will then be enrolled into this study and assigned to APD371 25 mg TID or 100 mg TID according to a randomization schedule. Randomization will be stratified by sex.

Randomization will take place across all study sites using a centralized master list held by the Sponsor clinical trial manger, in consultation with the Medical Monitor. When a site is ready to

Statistical Analysis Plan APD371-004

enroll a subject, they will contact the study manager to get the appropriate dose group assignment and unique subject number. The subject's identification number will be used on all of that subject's electronic case report forms (eCRF). Any subject identification numbers that are assigned will not be reused even if the subject does not receive treatment. All subjects must start treatment within 1 week of randomization.

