4.7.2. Time Points and Day Ranges

Since it is not always possible for all study participants to come in for their clinic visits on the exact day specified in the protocol schedule, the "Week" of a subject's visit will be defined by the relative day ranges described in Tables 1 to 3.

Table 1. Mapping for Endpoints Measured at Day 1, Wk 4, and Wk 8

Time Point	Target	Study Days
Baseline	Day 1	≤Day 1
Wk 4	Day 29	$2 \leq \text{Day} \leq 42$
Wk 8	Day 56	> Day 42

Table 2. Mapping for Endpoints Measured at Day 1 and Wk 8 or Wk 8 EOT

Time Point	Target	Study Days
Baseline	Day 1	≤ Day 1
Wk 8	Day 56	> Day 1
Wk 8 EOT	Day 57	>Day 1

Table 3. Mapping for Endpoints Measured at Day 1 and Wk 1 to Wk 8

Time Point	Target	Study Days
Baseline	Day 1	≤ Day 1
Wk 1	Day 8	$2 \le \text{Day} \le 11$
Wk 2	Day 15	$12 \le Day \le 18$
Wk 3	Day 22	$19 \le \text{Day} \le 25$
Wk 4	Day 29	$26 \le Day \le 32$
Wk 5	Day 36	$33 \le Day \le 39$
Wk 6	Day 43	$40 \le Day \le 46$
Wk 7	Day 50	$47 \le \text{Day} \le 53$
Wk 8	Day 56	> Day 53

If a subject has more than one assessment in a window, the assessment date closest to the target date will be selected. If a subject has 2 assessments that are equidistant from the target date, the later assessment will be selected.

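### SAP 4.7.1 sets an explicit pre-dose limit on the Day 1 Baseline for vital signs but not for ECG, and SAP 9.4 does not say which Wk 8 ECG is used

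*SAP*

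**What the plan says.** **ECG schedule (protocol 5.8.1, 6.3.1, 6.3.2).** ECGs are taken at Screening, on Day 1 before and 1.5 hours after the first daily dose, at Wk 8 (Day -1) before and 1.5 hours after the first daily dose, and at Wk 10. Protocol 5.8.1 also describes a triplicate pre-treatment ECG on Day -1, a day that its own collection schedule does not list.

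**Baseline (SAP 4.7.1).** Apart from pain scores, which use the Screening period, "Baseline value is defined as the Day 1 (randomization) measurement". The fall-back is: "If the Day 1 measurement is not available, the last non-missing pre-randomization measurement will be used as the Baseline value". The section then adds one sentence for one class of data: "For vital signs, where the time of the assessment is available, the last pre-treatment assessment on Day 1 will be the Baseline value". SAP 9.2.1 repeats the pre-treatment limit, again for vital signs.

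**Visit windows (SAP 4.7.2).** The Baseline window is Day 1 or earlier in all three mapping tables. When several assessments fall in a window, the closest date is used, and then: "If a subject has 2 assessments that are equidistant from the target date, the later assessment will be selected".

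**ECG analysis (SAP 9.4, SAP 13).** ECG values are listed, summarised, and summarised again as change from Baseline. The one ECG change table, Table 14.3.4.2, is titled for Week 8 and by visit. Neither place names the Day 1 record or the Wk 8 record.

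**The concern.** Tolerability and safety is the primary objective, and protocol 5.8.1 singles out PR and QTc increases from baseline as of particular interest. Baseline therefore matters for the ECG summary, and two Day 1 records compete for it, one of them taken on drug. If the 1.5-hour record served as Baseline, whatever changed between pre-dose and 1.5 hours on Day 1 would be subtracted from the later change. That includes any drug effect, but also time of day, meals and reading noise, so the distortion could go either way.

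The Wk 8 end of the comparison is open too. A change to the Wk 8 pre-dose ECG describes the time that the SAP calls trough for the pain scores. A change to the 1.5-hour ECG describes the time that it calls peak. These answer different safety questions.

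The SAP shows awareness of this problem elsewhere. Vital signs and the Active-Standing Test are summarised at every timepoint. For Wk 1 pain scores, SAP 3.3.2.1 notes that "APS scores cannot be accurately identified as pre-dose or post-dose, scores on Day 1 are disregarded". ECG has the same before-and-after structure and no such sentence.

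**Working it through.** The plan gives no figure to reproduce here, so the check applies the written rules to the ECG schedule.

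**1. Count of records (protocol 5.8.1).** 1 Screening + 2 Day 1 + 2 Wk 8 (Day -1) + 1 Wk 10 = 6 scheduled occasions. On or before Day 1: 1 + 2 = 3, of which 1 (Day 1, 1.5 hours) is post-dose. The Baseline window admits all 3.

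**2. SAP 4.7.1 applied to each case.**

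| Day 1 ECGs available | What the rule gives |
|---|---|
| Pre-dose only | Pre-dose |
| Pre-dose and 1.5 h | The rule speaks of one measurement and does not say which |
| 1.5 h only | 1.5 h; a Day 1 measurement exists, so the fall-back is not triggered |
| Neither | Last earlier record |

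The third row is the clearest gap. It needs no clock time and no tie-break. A Day -1 triplicate, if taken, would also be passed over whenever any Day 1 ECG exists.

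**3. SAP 4.7.2 when both Day 1 records exist.** Both are 0 days from the Day 1 target, so they tie on date. At Wk 8, with the visit on any of Days 54 to 58, both records are equally far from the Day 56 target (0 to 2 days). If the later-assessment sentence were applied within a day, it would pick the 1.5-hour ECG at both visits. The section, however, is introduced as a rule about visit days: "Since it is not always possible for all study participants to come in for their clinic visits on the exact day".

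**4. What a post-dose Baseline would do.** Let B0 = Day 1 pre-dose, B1 = Day 1 at 1.5 hours, W = the Wk 8 record. Then

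W − B1 = (W − B0) − (B1 − B0).

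The Day 1 acute shift, B1 − B0, is removed from the reported change. The documents give no ECG effect size, so the values below are assumptions: a 1.5-hour effect of 5, 10 or 20 ms, equal on both days, with no effect at trough.

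| Baseline → Wk 8 record | Reported change (ms) |
|---|---|
| Pre-dose → 1.5 h | +5 / +10 / +20 |
| Pre-dose → pre-dose | 0 / 0 / 0 |
| 1.5 h → pre-dose | −5 / −10 / −20 |
| 1.5 h → 1.5 h | 0 / 0 / 0 |

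If half the effect persisted at trough, the second row would read +2.5 / +5 / +10 and the third −2.5 / −5 / −10. The last two rows need a post-dose Baseline and are the unlikely readings. The first two rows differ only in the Wk 8 record, and the SAP does not choose between them.

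**5. Size of the added output.** Three change blocks are wanted (Day 1 1.5 h, Wk 8 pre-dose, Wk 8 1.5 h), and one Wk 8 change is already named: 3 − 1 = 2 extra. SAP 9.4 lists 7 intervals (RR, PR, QRS, QT, QTc, QTcB, QTcF): 2 × 7 = 14 interval-by-timepoint entries. With the six summary statistics of SAP 4, this is 14 × 6 = 84 lines per column.

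**The case against.** The strongest reply is that Baseline ordinarily means before dosing and that the SAP's own label points the same way. SAP 3.2 and 4.2 put randomization on Day 1, and a record taken 1.5 hours after the first dose always follows randomization. The protocol also lists the two Day 1 ECGs under separate pre-treatment and post-treatment headings, so an analyst has a basis for choosing. All of this stands as evidence of intent. It is not a rule. SAP 4.3 says "All subjects must start treatment within 1 week of randomization", so the randomization label is not tied to the first dose, and no sentence excludes the 1.5-hour record when it is the only one from Day 1.

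A reader might infer from the later-assessment sentence that the SAP prescribes an on-drug Baseline. The documents do not support that. The sentence is written for visit dates. SAP 9.2.1 summarises many same-day vital-sign records at all their timepoints, which would be impossible if the rule kept one record per day.

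A reader might also infer that vital signs are the only data with a protected Baseline. That is wrong as well: the pain-score Baseline uses diary entries before treatment (SAP 3.3.2.1, 8.2), and demographic and baseline characteristics use the last value before randomization (SAP 6.1). The gap concerns the Day 1 rule as it applies to ECG.

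Two further points stand in part. The missing pre-dose ECG is hypothetical, since the first dose is given at the site, and nothing shows that it occurred. The table title is also weak evidence that a timepoint is dropped: the vital-sign tables are titled by visit too, although their text calls for all timepoints. The table shells, the eCRF and the Schedule of Events are not visible in the public file and may settle some of this.

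**Conclusion.** The point holds as a minor gap in specification. For Day 1 measurements the SAP writes a pre-treatment limit for vital signs and omits it for ECG, although ECG is also recorded on both sides of the first dose. A post-dose ECG Baseline is not excluded, most clearly when the Day 1 pre-dose record is missing. Separately, the text does not say which Wk 8 ECG enters the change, and it names no Day 1 1.5-hour change. The general sentence in SAP 9.4 could cover both.

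The consequence is limited to one descriptive group summary in an open-label study of about 16 subjects. Individual ECG values are listed and tracings are reviewed on site, so a marked change in one subject would still be visible. No amount in ms can be claimed from the documents, and it would go too far to say that a post-dose Baseline was intended or used. The conclusion rests on the SAP text and table titles alone. Shells that already separate the timepoints would leave only the Baseline sentence to add.

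**What to change.** - **SAP 4.7.1 and 9.4:** state that ECG Baseline is the last record before the first dose. If the Day 1 pre-dose ECG is missing, use the last earlier record, never a post-dose one.
- **SAP 4.7.2:** state that the closest-date and later-assessment rules choose between visit dates, not between timed records of one visit.
- **SAP 9.4 and Table 14.3.4.2:** summarise change from Baseline separately for Day 1 1.5 h, Wk 8 pre-dose and Wk 8 1.5 h.
- **Protocol 5.8.1:** reconcile the Day -1 triplicate with the Day 1 pre-dose ECG in the collection schedule, and state in the SAP how the triplicate enters Baseline (for example, as the mean of the three).
- **If the table has already been run:** state in the study report which Day 1 and Wk 8 records were used.

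The cost is a few SAP sentences and two extra timepoint blocks for 7 intervals, or no extra blocks if the shells already hold them. No new data are needed.

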4.7.2. Time Points and Day Ranges

Since it is not always possible for all study participants to come in for their clinic visits on the exact day specified in the protocol schedule, the "Week" of a subject's visit will be defined by the relative day ranges described in Tables 1 to 3.

Table 1. Mapping for Endpoints Measured at Day 1, Wk 4, and Wk 8

Time Point	Target	Study Days
Baseline	Day 1	≤Day 1
Wk 4	Day 29	$2 \leq \text{Day} \leq 42$
Wk 8	Day 56	> Day 42

Table 2. Mapping for Endpoints Measured at Day 1 and Wk 8 or Wk 8 EOT

Time Point	Target	Study Days
Baseline	Day 1	≤ Day 1
Wk 8	Day 56	> Day 1
Wk 8 EOT	Day 57	>Day 1

Table 3. Mapping for Endpoints Measured at Day 1 and Wk 1 to Wk 8

Time Point	Target	Study Days
Baseline	Day 1	≤ Day 1
Wk 1	Day 8	$2 \le \text{Day} \le 11$
Wk 2	Day 15	$12 \le Day \le 18$
Wk 3	Day 22	$19 \le \text{Day} \le 25$
Wk 4	Day 29	$26 \le Day \le 32$
Wk 5	Day 36	$33 \le Day \le 39$
Wk 6	Day 43	$40 \le Day \le 46$
Wk 7	Day 50	$47 \le \text{Day} \le 53$
Wk 8	Day 56	> Day 53

If a subject has more than one assessment in a window, the assessment date closest to the target date will be selected. If a subject has 2 assessments that are equidistant from the target date, the later assessment will be selected.

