5.8 Electrocardiography

5.8.1 12-lead Safety Electrocardiograms

Safety 12-lead ECGs will be recorded from an ECG machine and will be printed and reviewed on site by the Investigator or designee. Typically, all 12-lead ECGs will be obtained as single tracings, with the exception of the pre-treatment ECG obtained on Day -1, which will be a triplicate recording. If a 12-lead ECG shows an abnormality, then two additional ECGs should be obtained as soon as possible for confirmation. Abnormalities of particular interest include increased PR or corrected QT (QTc) intervals, either absolute prolongations or clinically noteworthy increases from baseline values.

Electrocardiograms will be recorded with subjects resting in the supine position. Subjects will have been in the supine position for 10 minutes prior to ECG recording, which will be performed prior to any vital sign measurement and/or blood draw that may be scheduled at the same time point.

Intervals to be provided on the confirmed read for each 12-lead ECG are: RR, PR, QRS, QT, QTc, QTcB, and QTcF. All interval measurements will be made from a single lead (lead II). If lead II is unsuitable for measurement, the following lead progression will be used: I, V4, V5, V3, any suitable lead.

The Investigator will be responsible for review and interpretation of 12-lead ECGs on site and for determining if the ECG is normal, abnormal clinically insignificant, or abnormal clinically significant. Findings will be documented in the eCRF. This information will be used in the ongoing safety review during the conduct of the study.

A 12-lead ECGs will be collected at Screening; at the start of Wk 0 (Day 1) and at Wk 8 (Day -1) prior to and 1.5 hours after the first daily dose; and at the Follow-up Visit at Wk 10. 12-lead ECGs will be collected prior to any vital sign measurement and/or blood draw that is scheduled at the same time point.

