5.9.4 C-reactive Protein and other Biomarkers

Separate blood samples (a total of 20 mL) for high sensitivity analysis of CRP will be collected at screening, pre-dose at Day 1, Week 4 and Week 8 (Day -1), and Week 10 (Follow-up).

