6.4 Early Termination Procedures

- Physical examination (abbreviated examination including body weight and evaluation of changes to previously observed abnormal findings)
- Vital signs and Active-Standing Test
- 12-lead ECG
- Serum hCG pregnancy test (females only)
- Final PK blood sample
- Clinical laboratory tests (to include hematology, serum chemistry, coagulation, HsCRP, and urinalysis)
- Abdominal Pain Score
- Record AEs
- Record concomitant medications

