6.5 Wk 10 Follow-up Visit Procedures

Subjects will return to the study site on an outpatient basis for a Follow-up Visit.

- Physical exam (abbreviated examination including body weight and evaluation of changes to previously observed abnormal findings)
- Vital signs and Active-Standing Test
- 12-lead ECG
- Serum hCG pregnancy test (females only)
- Clinical laboratory tests (to include hematology, serum chemistry, coagulation, HsCRP, and urinalysis)
- Record AEs
- Record concomitant medications

The Principal Investigator and study site staff should exert every effort to secure subject attendance to the Follow-Up visit. Three attempted telephone contacts should be documented by study personnel before a subject can be considered lost to follow-up. Furthermore, key research personnel should mail a certified letter to the subject's address if no response to 3 telephone contacts remain unanswered. If the subject or a family member does not respond, the certified letter receipt should be filed in the individual's research record with a copy of the letter sent.

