4.7.3. Missing Data

As described in Section 8.3, in responder analyses, subjects with missing data will be classified as non-responders. Otherwise, there will be no imputation of missing data.

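### SAP visit windows leave Wk 8 open-ended: when the scheduled record is missing, an off-drug Wk 10 value can be reported as Wk 8, and an early-termination value as Wk 4 or Wk 8

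*SAP*

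**What the plan says.** SAP 4.7.2 allows for visits that fall off schedule: the week of a subject's "visit will be defined by the relative day ranges described in Tables 1 to 3".

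- Table 1, for endpoints at Day 1, Wk 4 and Wk 8: Wk 4 is Days 2 to 42 (target Day 29). Wk 8 is any day after Day 42 (target Day 56).
- Table 2, titled "Mapping for Endpoints Measured at Day 1 and Wk 8 or Wk 8 EOT": Wk 8 (target Day 56) and Wk 8 EOT (target Day 57) are both any day after Day 1.
- Table 3, weekly: Wk 8 is any day after Day 53.

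The selection rule is: "If a subject has more than one assessment in a window, the assessment date closest to the target date will be selected". Ties go to the later record. No table has a follow-up or early-termination row, and nothing refers to the last dose.

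The protocol schedules records that these windows can capture. Dosing runs for 56 days (6.3), and the visit tolerance, including Wk 10, is 2 days either way (5.15). Labs are drawn at Wk 10 and at early termination (5.9). ECGs are taken at Screening, and at Day 1 and Wk 8 (Day -1) "prior to and 1.5 hours after the first daily dose; and at the Follow-up Visit at Wk 10" (5.8.1); early termination adds another (6.4). HsCRP is drawn at Wk 10 (5.9.4, 6.5) and is part of the early-termination labs (6.4).

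The SAP's own CRP endpoint (3.3.2.5) lists only Baseline, Wk 4 and Wk 8. SAP 9.3 limits the lab shift tables to on-treatment visits. The by-visit lab, CRP and ECG summaries carry no such limit.

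**The concern.** A window that fixes the week by study day works only if every scheduled record has a row of its own, or is excluded. Here the Wk 10 and early-termination records have neither. When the intended record is missing, the next available one takes its place however far it lies from the target day and whether or not the subject is still on drug.

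Safety is the primary objective, and labs and ECG are safety outputs. An off-drug value shown as Wk 8, or a first-week termination value shown as Wk 4 or Wk 8, misdescribes exposure at that visit. For CRP, SAP 8.6 regresses change in CRP on change in peak AAPS at Wk 8, or the reverse. If a Wk 10 CRP were admitted, an off-drug CRP would be paired with an on-drug pain score.

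**Working it through.** **Assumptions.** The SAP does not name the endpoints that use each table. From the visit schedule, labs and CRP fit Table 1. ECG fits Table 2, which is also consistent with SAP Table 14.3.4.2 (change from baseline at Week 8). No day number is given for Wk 10; Day 70 and Day 71 are both tried.

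**The SAP's own cut points.** Each upper bound is the midpoint of adjacent target days, rounded down. Table 1: (29 + 56)/2 = 42.5, giving 42. The same rule applied to the Table 3 targets (8, 15, 22, 29, 36, 43, 50, 56) gives 11, 18, 25, 32, 39, 46 and 53. All match the SAP. The rule was not carried on to a follow-up visit after Wk 8.

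**Wk 10 records.** Day 70 ± 2 is Days 68 to 72, which is 12 to 16 days after Day 56. Day 71 ± 2 is Days 69 to 73, which is 13 to 17 days after. Every one of these days satisfies > 42, > 1 and > 53, so it is a Wk 8 day in all three tables.

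- Lab records on Days 29, 56 and 71: Day 56 is selected for Wk 8.
- Lab records on Days 29 and 71 only: Day 71 is selected for Wk 8.
- Completers in general: a Wk 8 visit on Days 54 to 58 is at most 2 days from target, while Wk 10 is at least 68 − 56 = 12 days away. The Wk 8 record always wins.

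**Early-termination records, with no closer record.**

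| Record | Day | Label | Days before target |
|---|---|---|---|
| Lab (Table 1) | 2 | Wk 4 | 29 − 2 = 27 |
| Lab (Table 1) | 5 | Wk 4 | 29 − 5 = 24 |
| HsCRP (Table 1) | 8 | Wk 4 | 29 − 8 = 21 |
| Lab (Table 1) | 14 | Wk 4 | 29 − 14 = 15 |
| ECG (Table 2) | 5 | Wk 8 and Wk 8 EOT | 56 − 5 = 51 (Wk 8) |
| ECG (Table 2) | 42 | Wk 8 and Wk 8 EOT | 56 − 42 = 14 (Wk 8) |

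The HsCRP row starts at about Day 8 because the CRP outputs use the Efficacy population, which needs 7 days of APS (SAP 4.5). A termination lab on Days 30 to 42 after a Day 29 visit is not used, because Day 29 is closer.

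**Weight.** One record is 1/8 = 12.5% of a mean with 8 per arm, or 1/10 = 10% with 10 per arm (the maximum of 20 randomized). That is a share, not an estimate of bias.

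**The case against.** Several points on the other side are sound.

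- **The table match is inferred.** SAP 4.7.2 names no endpoints, and the protocol lists no ECG at the Wk 8 End of Treatment visit (6.3.7). ECGs are also taken twice on Day 1 and at Wk 8 (Day -1), so they need nominal timepoints that a day-only map cannot supply. The ECG result is therefore conditional.
- **CRP at Wk 10 may not be an input.** SAP 3.3.2.5 and 8.6 list only Baseline, Wk 4 and Wk 8. On that reading the off-drug scatterplot example disappears. The documents do not settle it.
- **Some carry-in may be intended.** SAP 8.6 analyses CRP at Wk 8/EOT, which could mean a last-on-treatment value. That would not explain a Wk 10 value at Wk 8 or a Day 5 lab at Wk 4.
- **A programmer might keep Wk 10 by its visit name.** SAP 9.2.1 does list Wk 10 separately for vital signs. SAP 9.3 and 9.4 do not for labs and ECG, and the rule as written goes by day.

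A reader might also infer that the windows contradict SAP 4.7.3, which says, after the responder rule, "Otherwise, there will be no imputation of missing data". They do not: placing an observed value in an analysis window is visit assignment, not imputation. Nor can a termination ECG become Wk 4, because Table 2 has no such row.

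**Conclusion.** The point stands as a minor-to-moderate correction. Applied literally, the rule gives a wrong label in two situations: a missing Wk 8 record with a Wk 10 record present, and an early termination with no closer record. The first result is firm for labs if they use Table 1, as their schedule indicates (the Wk 10 day falls after Day 42 under either numbering). It is conditional on Table 2 for ECG, and on the Wk 10 sample being an input for CRP. The second holds for labs and HsCRP under Table 1, and for ECG only under Table 2.

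The reach is limited. There is no primary endpoint, completers' values are correct, the lab shift tables are protected, and lab and ECG values remain in the listings. Fecal calprotectin is not scheduled at Wk 10 or early termination, and AAPS has its own derivation, so neither is affected. The documents give no rate of missed Wk 8 records or early terminations, so no probability or size of bias can be claimed. It would go too far to say that the Wk 8 results as a whole are contaminated.

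**What to change.** 1. State that a record from the nominal Wk 10 visit never fills an on-treatment week, and show it in a Follow-up row.
2. Cap Wk 8 and Wk 8 EOT at Day 63 in Tables 1 and 2. This extends the SAP's own midpoint logic: (56 + 70)/2 = 63, and (56 + 71)/2 = 63.5 rounds down to the same day. It excludes every Wk 10 day from 68 to 73 but keeps a genuine late Wk 8 visit, for example on Day 61. Footnote days since last dose.
3. Start Table 1 Wk 4 at Day 15, since (1 + 29)/2 = 15, and Table 2 Wk 8 at Day 43, the SAP's own Table 1 cut. An early-termination record outside these bounds goes in an Early termination row. If Wk 8/EOT is meant as a last-on-treatment-value summary, label it so and keep it apart from Wk 8.
4. Name the endpoints that use each table.
5. Report this as a change made after database lock, with the number of records whose row changed. Protocol Section 8 already requires SAP changes to be listed and explained in the study report, and SAP Amendment 1 was itself written after lock.

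The cost is an edit to two small tables, a few sentences, and a rerun of the lab, CRP and ECG summaries. A few Wk 4 or Wk 8 values become missing, and the change is post hoc. Some distance from target remains: a termination record on Day 20 still counts as Wk 4 (29 − 20 = 9 days early) and one on Day 44 as Wk 8 (56 − 44 = 12 days early), which is why the footnote is needed.
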